### 5.5 Sensitivity analyses

No adjustments will be made in the primary analyses other than for stratification variables.

Sensitivity analyses are made with:

- Adjustment for baseline differences for those baseline characteristics with unequal/skewed baseline means and that can thus be associated with the outcome. Baseline characteristics in this case include (in addition to stratification variables) diagnosis, age, site and functioning) and self-reported outcome measures at baseline. Baseline tests will not be used exclusively in judging whether to include in the sensitivity analysis. Inclusion will be based on whether the groups are different to the extent that it could affect the analyses. The selection will be guided by CH.
- Imputations of missing values representing “worst” and “best” case of imputations. We will make two analyses: one where we in both groups replace imputations with “worst” case defined as the 90 percentiles from the imputed value and one where we in both groups replace imputations with “best” case defined as the 90 percentiles from the imputed value.
- The observed data.

Sensitivity analyses will be made for the primary outcome.

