#### 3.2 Randomization

From the protocol paper ([name], et al. 2020):

After baseline data are obtained, the participants are randomly assigned to either the control (standard mental healthcare) or experimental group (MA&R + standard mental healthcare) with a 1:1 allocation using the randomization module in REDCap (Research Electronic Data Capture) [44, 45]. The randomization sequence was generated by a researcher employed outside the research team and entered to RedCap. The randomization is stratified by sex. Varying block sizes, unknown to the research team, are used. To ensure concealment, the randomization schedule is stored away from the research team and the block sizes are not disclosed. The allocation is performed by the researcher, who informs the participants and the counsellors and who assigns participants to the interventions.”

Participants gave informed consent (verbal and written) and filled out the baseline questionnaire before randomization.

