### 3.3 Sample size calculation

Below numbers are retrieved from the protocol paper ([name] et.al 2020).

- Type 1 error set at: 0.05 ( $\alpha$ )
- Power: 0.80 ( $\beta$ )
- Difference in mean: 3 points
- within group standard deviation (SD): 6

From the protocol paper ([name] *et al.*, 2020): “The sample size is calculated based on the primary hypothesis to detect a minimal but clinically significant difference between the intervention group and the control group on POES-S (increased engagement in meaningful activities). In a recent RCT testing, the intervention Balancing Everyday Life (BEL) in a similar population as that in this study, Eklund et al. found a small effect of 1.4 points measured on POES-S ( $d = 0.27$ ) [21]. As MA&R has a more comprehensive format (in terms of duration and costs) than BEL, the clinically significant difference between the study groups is set to 3 points, corresponding to a moderate effect size (Cohens  $d = 0.5$ ). Based on the BEL trial, we assume the standard deviation in the study population to be 6. To achieve a statistical power of 80% and a significance level of 5%, a total of 128 participants must be included in this study; 64 in each group to detect this difference.”

No interim analyses were planned.

There were no guidelines for stopping the trials early.

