### 5.3 Specification of outcomes and timing

See appendix 1 for an overview over outcomes and timing.

- Activity engagement (measured by POES-S) at eight months follow up is the primary outcome (end point comparison)
- Personal recovery (measured by QPR), quality of life (measured by MANSA) and levels of functioning (measured by WHODAS-12) at eight months follow up are secondary outcomes (end point comparisons)
- WHODAS-36 subscales, WHODAS-36 total score and health related quality of life (EQ-5D-3L) at eight months follow up are exploratory outcomes (end point comparison).

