#### 5.4.1 Baseline variables

The chi test is used to test for differences in nominal baseline variables (sex, education, housing status, marital status, diagnosis, employment status) and the t-test is used to test for differences in ordinal/continuous baseline variables (age, activity engagement, functioning, personal recovery, quality of

life). If the test assumptions in the latter are not met, a non-parametric test will be performed instead (e.g. Kruskal Wallis or Mann Whitney U test).

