#### 5.4.2 Self-reported outcomes

Primary, secondary and exploratory outcomes are calculated and presented in means of scores at 8 months follow-up. In the protocol we wrote:

“The main outcome measure is activity engagement, measured by POES-S. To test the research hypothesis, the differences between the intervention group and the control group will be analyzed using ANOVA to determine the statistical significance. Effect sizes to judge clinical relevance will be calculated by Cohen’s d. In accordance with the intention-to-treat principles,

“multiple multivariate imputations” will be used and all co-variates of supposed prognostic significance will be used to impute a distribution of missing data.

The continuous power measurements will be analyzed with a repeated measurement model in mixed model analyses with unstructured variance. The prerequisite for using this analysis and for the use of multiple imputations is that data are missing at random or data missing completely at random as opposed to non-ignorable nonresponse. This distinction is important as repeated measurements and multiple imputations are both models based on a statistical estimation of non-existent responses, and the prerequisites for this estimation must be met for the analyses to be valid.” ([name] et al, 2020)

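### The primary POES-S analysis excludes the baseline POES-S score, which is already collected, and so gives up precision; a mixed model is also left in the text without a role

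*SAP*

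**What the plan says.** The primary outcome is POES-S at eight months, defined in SAP section 5.3 as an end-point comparison. Section 5.4.2, quoting the protocol, assigns the test: "To test the research hypothesis, the differences between the intervention group and the control group will be analyzed using ANOVA". Section 5.5 limits the covariates: "No adjustments will be made in the primary analyses other than for stratification variables". Section 3.2 gives a single stratification factor: "The randomization is stratified by sex".

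Baseline scores exist for every randomised participant in principle. Sections 3.1 and 3.2 place the baseline questionnaire before randomisation, section 4.4 says the self-reported outcome measures at baseline will be summarised, and section 5.4.1 lists activity engagement among the baseline variables.

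These scores have one route into an adjusted analysis of the treatment effect. Section 5.5 lists baseline self-reported measures as candidates for an adjusted sensitivity analysis, under this rule: "Inclusion will be based on whether the groups are different to the extent that it could affect the analyses". The choice is to be guided by one contributor.

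The same protocol quotation in section 5.4.2 then introduces a second model: "The continuous power measurements will be analyzed with a repeated measurement model in mixed model analyses with unstructured variance".

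**The concern.** A baseline measurement of the outcome is usually the strongest single predictor of follow-up. Because it is recorded before randomisation, adjusting for it introduces no bias and costs one degree of freedom. Leaving it out keeps variation in the comparison that could have been removed.

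The rule for the sensitivity analysis does not make up for this. It turns on observed imbalance between the arms, whereas the precision gain comes from the correlation between baseline and follow-up and is there whether or not the arms are balanced. A well-balanced trial might report no baseline-adjusted result at all, and whether one appears depends on a judgement made after the baseline data are seen.

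The mixed-model sentence adds a smaller difficulty. The SAP does not say which outcomes it covers, what contrast it estimates, or how it ranks against the ANOVA, and it is not among the sensitivity analyses in section 5.5. Section 3.1 says data were collected only twice. A repeated-measures model would therefore have to use the baseline score as one of its two measurements, which sits awkwardly with a rule that keeps baseline out of the primary analysis.

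**Working it through.** **Inputs.** Section 3.3: difference 3 points, within-group SD 6, 64 per arm, power 80%. Section 5.1: two-sided 5%. The SAP gives no correlation *r* between baseline and 8-month POES-S; values of 0.3, 0.5 and 0.7 are assumed, with 0.1 and 0.2 added as low cases.

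**Step 1: reproduce the plan's figure.** The unadjusted standard error is SE = 6 × √(2/64) = 1.061. The noncentrality is 3/1.061 = 2.83. With 126 degrees of freedom (critical value 1.979), the two-sample *t*-test has power 80.1%. With 63 per arm it has 79.5%, so 64 per arm is the smallest size that reaches 80%. The stated 128 is confirmed for an unadjusted comparison. The 95% CI half-width is 1.979 × 1.061 = 2.10 points.

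**Step 2: adjust for baseline.** The residual SD becomes 6 × √(1 − *r*²), so SE = 1.061 × √(1 − *r*²). Group, baseline and sex leave 124 degrees of freedom. Any gain from sex itself is ignored.

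| Assumed *r* | SE | CI half-width | Power |
|---|---|---|---|
| unadjusted | 1.06 | 2.10 | 80.1% |
| 0.1 | 1.06 | 2.09 | 80.5% |
| 0.2 | 1.04 | 2.06 | 81.7% |
| 0.3 | 1.01 | 2.00 | 83.7% |
| 0.5 | 0.92 | 1.82 | 90.0% |
| 0.7 | 0.76 | 1.50 | 97.6% |

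The variance removed is *r*²: 9%, 25% and 49% at 0.3, 0.5 and 0.7.

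**Step 3: how often the two analyses disagree.** Arm differences at baseline and follow-up were simulated as bivariate normal with correlation *r*, a true difference of 3 and critical value 1.96, with at least one million trials per *r*.

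| Assumed *r* | Only adjusted significant | Only unadjusted significant | Verdicts differ |
|---|---|---|---|
| 0.3 | 5.2% | 1.7% | about 7% |
| 0.5 | 10.9% | 1.3% | about 12% |
| 0.7 | 17.3% | 0.3% | about 18% |

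All figures assume complete data on 128 participants.

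**The case against.** The strongest reply is that nothing here is wrong. Sections 3.2, 3.3, 5.3, 5.4.2 and 5.5 agree with one another: stratify by sex, size on an unadjusted SD, compare at the end point, adjust only for stratification. The analysis meets its own power target, and because the primary model is fixed, the imbalance judgement cannot choose the primary verdict or inflate its type I error. All of that stands, and the point is accordingly one of efficiency.

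The gain also rests on an assumed correlation. Follow-up comes about eight months later, after an intervention meant to change the score, so a low value cannot be ruled out; at 0.1 or 0.2 the gain is under two points of power. The disagreement figures are largely the power gain seen another way and should not be counted as a second harm. No loss has been calculated for the secondary outcomes. These limits also stand.

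Changing a published primary model late has a price in credibility. Enrolment ended in August 2020 and treatment lasts about eight months, which points to about April 2021, before any late follow-up; the SAP is dated July 2021. Much or all of the outcome data may already be in. This bears on how the change is made and documented.

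Multiple imputation under sections 5.4.2 and 5.9 may draw on baseline POES-S. That helps with missing outcomes but does not remove baseline variation from the observed ones.

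Finally, the mixed-model sentence lies inside a protocol quotation, and the ANOVA can reasonably be read as the primary test. The sentence still needs a role, because this SAP describes itself as the detailed version of the plan and neither drops nor ranks that model.

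**Conclusion.** The concern holds and should be fixed. The plan explicitly excludes from its primary model a prognostic covariate already in hand, and makes its use elsewhere depend on judged imbalance. The cost is precision: about 3.5 points of power at a correlation of 0.3, about 10 at 0.5 and about 17 at 0.7, with the confidence interval 5%, 13% or 29% narrower after adjustment (from 2.10 to 2.00, 1.82 or 1.50). The result rests on the SAP's SD of 6, complete data and an assumed correlation; if the correlation is 0.2 or less, little is lost. There is no bias, and the sample size of 128 is not in error. The unranked mixed model is a secondary matter of clarity.

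**What to change.** - In section 5.4.2, define the primary analysis as a linear model of 8-month POES-S on randomised group, baseline POES-S and sex, fitted in the multiply imputed data. Amend the adjustment rule in section 5.5 to match.
- Treat each secondary outcome the same way, with its own baseline score where one was collected.
- Keep the published unadjusted ANOVA as a sensitivity analysis, reported whatever the baseline balance.
- Delete the mixed-model sentence, or label that model a sensitivity analysis, name the outcomes it covers and state its contrast as the group difference at 8 months.

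No new data are needed. The cost is a late replacement of the published primary model. The amendment should therefore be dated, made before any unblinded outcome analysis, and reported as a departure from the published plan, as section 5.2 already provides for major deviations. If outcomes have already been examined by arm, keep the ANOVA as primary and report the baseline-adjusted model unconditionally as a sensitivity analysis.

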### 3. Study Methods

#### 3.1 Trial design

A multicenter two arm, parallel randomized controlled trial. Eligible participants were individuals with psychiatric disabilities, who were treated in one of three community mental health centers in Mental Health Center Copenhagen, or were citizens in the municipalities of Copenhagen, Svendborg or Odense. Included participants were allocated with a 1:1 ratio to either Meaningful Activities and Recovery (MA&R) a novel rehabilitation intervention, in addition to usual care, or usual care alone. The enrollment started at September 2018 and lasted to August 2020. MA&R lasts for about eight months and consists of 11 group sessions and 11 one-to-one sessions.

From the protocol ([name] et al, 2020)

“MA&R is delivered by a peer worker and an Occupational therapist. In addition to the planned sessions, the participants are offered individualized support to engage in meaningful activities. The MA&R is a manualized intervention, with a workbook developed for the participants to support learning and personal exploration. MA&R utilized various methods such as didactic presentations, peer exchange, direct experiences with activities and personal exploration. The MA&R contains two courses: MA&R I and MA&R II which complement each other. In MA&R I, the participants can explore and identify meaningful activities, while MA&R II supports anchoring new activities and habits in everyday life.”

Data was collected twice, baseline before randomization and at follow up, at the end of the intervention.

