## 4.4 Baseline characteristics

Sex, age, housing/marital status, educational level, diagnosis, work status, functional level (assessed by researcher). Register-based and self-reported baseline outcome measures will also be summarized.

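### The adjusted sensitivity analysis of POES-S chooses covariates by observed arm difference without a threshold, so its model is not fixed in advance and baseline POES-S can be left out

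*SAP*

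**What the plan says.** Section 5.5 of the SAP fixes the primary adjustment: "No adjustments will be made in the primary analyses other than for stratification variables". Section 3.2 names one such variable: "The randomization is stratified by sex".

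Section 5.5 then plans, for the primary outcome, a sensitivity analysis adjusted for "those baseline characteristics with unequal/skewed baseline means and that can thus be associated with the outcome". The candidates are listed: "Baseline characteristics in this case include (in addition to stratification variables) diagnosis, age, site and functioning) and self-reported outcome measures at baseline". The self-reported measures include baseline POES-S. Baseline significance tests are not to be the only guide. The operative rule is "Inclusion will be based on whether the groups are different to the extent that it could affect the analyses", with the selection guided by one contributor, identified by initials.

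The section gives no size of difference, no measure of difference and no separate test of prognostic value. It does not say when, or with what knowledge of outcomes, the choice is made.

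**The concern.** The analysis is there to show whether baseline differences could explain the primary result. It does that best when a reader can see beforehand which model will be fitted. Here two analysts could read the same rule and the same baseline table and enter different covariates. One might act on a large baseline difference, the other on a difference that moves the POES-S contrast.

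The rule also ties association with the outcome to imbalance. Under randomisation stratified by sex alone, any other imbalance arises by chance, and its size says nothing about how well the variable predicts POES-S. A strong predictor that is balanced can be left out and a weak one that is unbalanced can enter. Baseline POES-S is the candidate for which this matters most. Leaving it out costs precision, and leaving the choice open leaves room for decisions after outcomes are known.

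One candidate also needs clarifying. Functioning is listed apart from the self-reported measures. Section 4.4 has a "functional level (assessed by researcher"), while section 5.3 has "levels of functioning (measured by WHODAS-12").

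**Working it through.** **Inputs from the SAP (3.3, 5.1, 3.1):** difference 3 points, SD 6, two-sided 5%, power 80%, 1:1 allocation, 64 per arm. **Assumed, because the SAP does not give them:** baseline-to-8-month POES-S correlation r = 0.3, 0.5 or 0.7; the cut-offs below; complete data.

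**1. The plan's own figure.** With d = 3/6 = 0.5, the two-sample t-test needs 63.8, so 64 per arm and 128 in total, as stated. Power at 64 per arm is 80.1%. The standard error is 6 × √(2/64) = 1.06 points.

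**2. How often baseline POES-S would enter.** Under valid randomisation the chance that the standardised difference exceeds t is 2 × [1 − Φ(t / √(2/64))], with √(2/64) = 0.177.

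| Cut-off | Enters | Omitted |
|---|---|---|
| 0.1 SD | 57% | 43% |
| 0.2 SD | 26% | 74% |
| 0.3 SD | 9% | 91% |
| p < 0.05 (about 0.35 SD) | 5% | 95% |

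The unstated cut-off largely decides the model.

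**3. What always including it would give.** The residual SD is 6 × √(1 − r²) = 5.72 / 5.20 / 4.28. The standard error is 1.01 / 0.92 / 0.76, and normal-approximation power is 84 / 90 / 98%.

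**4. Selection by difference.** Simulated two-arm trials, 64 per arm, comparing the unadjusted contrast with ANCOVA on baseline POES-S. The selective rule enters it only above 0.2 SD:

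| r = 0.3 / 0.5 / 0.7 | Null rejection | Power | 95% CI width (points) |
|---|---|---|---|
| Never included | 5% | 80% | about 4.2 |
| Above 0.2 SD only | 4.5 / 3.7 / 2.5% | 81 / 84 / 88% | 4.15 / 4.06 / 3.89 |
| Always included | about 5% | 83 / 90 / 98% | 4.01 / 3.64 / 3.00 |

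(Never-included width: 2 × 1.98 × 1.06 = 4.2.)

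**5. A second reading of the rule.** Suppose baseline POES-S enters only if it shifts the contrast by more than 0.3 points (assumed). It is then omitted in 67 / 44 / 32% of trials. The two readings disagree on its entry in 13 / 30 / 42%, but at a true difference of 3 points they disagree on significance in only about 1 / 4 / 7%.

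**6. What a tolerated imbalance leaves in the estimate.** A baseline difference of 0.2 SD is 0.2 × 6 = 1.2 points. Not adjusting for it leaves r × 1.2 = 0.36 / 0.60 / 0.84 points, against a target of 3.

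**7. Cost of a fuller set.** Section 3.1 recruits from "one of three community mental health centers in Mental Health Center Copenhagen, or were citizens in the municipalities of Copenhagen, Svendborg or Odense", which can be counted as 4 to 6 sites. Assume 3 to 6 diagnosis groups. Baseline POES-S, age and functioning use 3 degrees of freedom. The additions to sex are then 3 + 3 + 2 = 8 up to 3 + 5 + 5 = 13, leaving 125 − 8 = 117 down to 125 − 13 = 112 residual. If everything beyond POES-S is worthless, the standard error relative to sex alone is roughly √[(1 − r²)(1 + q / residual df)]. At r = 0.3 this is √(0.91 × 1.068) = 0.99 for q = 8 and √(0.91 × 1.116) = 1.01 for q = 13. At r = 0.5 with q = 13 it is √(0.75 × 1.116) = 0.91.

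**The case against.** The best defence is that this is labelled an adjustment for baseline differences. It asks whether imbalance explains the result, and for that question dropping a balanced covariate is deliberate and hardly moves the estimate. The phrase about affecting the analyses can also be read as imbalance combined with prognostic effect, which is more sensible than imbalance alone. Both points have force, and they limit the size of the concern. They do not remove it: on either reading no threshold is stated and the choice remains a judgement.

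Baseline POES-S may also be used elsewhere. Section 5.4.2 quotes a repeated-measures mixed model, and section 5.9 uses auxiliary variables for imputation. Neither fixes it as a covariate in this adjusted model.

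On functioning, the separate listing in 5.5 mirrors 4.4 and suggests the researcher-assessed level. Section 5.4.1 uses the word more loosely, so one clarifying phrase is enough.

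A reader might infer more than the text supports:

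- *That the primary result is compromised.* It is not; its adjustment is fixed separately.
- *That the rule inflates type I error.* Applied mechanically to baseline POES-S it does the opposite.
- *That the analysis cannot be reproduced.* Once the chosen covariates are reported it can be refitted; it just cannot be predicted beforehand.
- *That one contributor's guidance is improper.* The SAP section on contributors' roles is not available, so nothing can be concluded.

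**Conclusion.** The concern holds for one supporting analysis of the primary outcome. Section 5.5 states a selection rule that turns on observed difference, without a threshold and by judgement. The model is therefore open, and baseline POES-S may be absent from it.

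The statistical loss is one of precision and conservatism. It is small at a correlation of 0.3 (power about 81% against 83%) and material at 0.7 (88% against 98%). With baseline POES-S as the only candidate, power does not fall below the planned 80%. These figures illustrate and do not measure: they rest on assumed cut-offs and correlations, complete data and a single candidate covariate, and they do not model the imputation. The defect in the text depends on none of them. It is worth correcting because the remedy is cheap, not because the trial's main conclusion is at risk.

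**What to change.** Before outcomes are analysed by arm, replace the selection sentences in 5.5 with a named model, for example: *The adjusted sensitivity analysis of POES-S at 8 months includes sex, baseline POES-S and [those of age, diagnosis, site and functioning named here on prognostic grounds], whatever the observed balance.* State whether functioning means the researcher-assessed level or WHODAS, and give the levels of site and diagnosis if they are included. An adjustment driven by observed imbalance may be kept if it is labelled exploratory. If outcomes have already been analysed by arm, date the change and report it as a deviation, as 5.2 provides.

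The cost is SAP wording and a few degrees of freedom; the variables are already named as candidates and no new data are needed. The downside is real at low correlation. At about 0.3 with many site and diagnosis levels, the full set gains no power and the interval can be about 1% wider than with sex alone. The only benefit there is a prespecified model, which is a reason to keep the list short.

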## 4.3 Withdrawal

### 4.3.1 Withdrawal from treatment

It was always possible to drop out of treatment/intervention. Hereafter one could choose to participate in follow-up (answer questionnaire etc.) or not. If a person in the intervention group dropped out of treatment this was registered (+ preferably reason if possible). If the participant was in the control group drop out of treatment as usual was not registered as it was not possible to get this information.

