# 5. Statistical principles and analysis

## 5.1. Confidence intervals and p-values

The two-sided significance level for statistical tests will be 5 %. Differences in means and proportions will be presented with a 95% confidence interval (CI) and a p-value. All primary, secondary and exploratory measures will be presented.

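### Both missing-data stress tests in SAP 5.5 shift the two arms the same way, so no planned analysis tests a departure from missing at random that differs between arms

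*SAP*

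**What the plan says.** Section 5.5 lists three sensitivity analyses for the primary outcome: adjustment for baseline differences, a worst-case and best-case replacement of imputed values, and an analysis of the observed data. The worst/best pair is two runs, each introduced as "one where we in both groups replace imputations with" a percentile of the imputed value. No run changes one arm only, and none moves the arms in opposite directions.

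Section 5.4.2, quoting the published protocol, gives the condition on which the main analysis rests: "The prerequisite for using this analysis and for the use of multiple imputations is that data are missing at random" or missing completely at random. It adds that the analyses are valid only if this is met. Section 5.9 describes the imputation model and allows for skewed dropout. No expected loss rate is stated.

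Section 5.5 gives the same 90th percentile for worst and best. That is a separate wording error. Here it is taken as corrected to the 10th percentile for worst and the 90th for best, because Table 1 says a higher POES-S score is better.

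**The concern.** The quantity of interest is a difference between arms. Lowering, or raising, the imputed scores in both arms together changes that difference only to the extent that the arms have different amounts of missing data or different imputation spread.

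The departure from missing at random that biases a comparison is one that differs by arm: for instance, MA&R non-responders doing worse than the imputation model predicts while control non-responders do as predicted. Section 5.5 has no run of that kind. The observed-data analysis does not fill the gap, because it also treats the missingness as ignorable. The SAP names the assumption as essential but does not stress it in the direction that matters most for the effect estimate.

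**Working it through.** **Inputs from the SAP.** "Difference in mean: 3 points" and "within group standard deviation (SD): 6" (section 3.3); two-sided 5% level (section 5.1); 1:1 allocation (section 3.1); 64 per arm (section 3.3).

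**Assumptions, because the SAP gives no figure.** Missing fractions of 10% to 30% per arm; baseline R-squared 0.25; percentile fills at the 10th and 90th.

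**Step 1: the plan's own figure.** The normal approximation gives n = 2 × (1.960 + 0.842)² × 6² / 3² = 62.8, so 63 per arm. The t-test version gives 63.77, so 64 per arm and 128 in total, as stated.

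**Step 2: effect of a fill on the difference.** Let m_T and m_C be the missing fractions in MA&R and control, and s_T and s_C the SDs of the imputation distributions. The 90th percentile lies 1.2816 SDs above the centre and the 10th the same distance below.

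- Same direction: change = ±1.2816 × (s_T·m_T − s_C·m_C)
- Opposite directions: change = ±1.2816 × (s_T·m_T + s_C·m_C)
- MA&R only, worst: change = −1.2816 × s_T·m_T

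**Step 3: numbers.** With R-squared 0.25, s = 6 × √0.75 = 5.20 in both arms, so each filled score moves by 1.2816 × 5.20 = 6.66 points. Starting from a difference of 3:

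| Missing MA&R / control | Both worst | Both best | MA&R only worst | MA&R worst, control best | MA&R best, control worst |
|---|---|---|---|---|---|
| 10% / 10% | 3.00 | 3.00 | 2.33 | 1.67 | 4.33 |
| 20% / 20% | 3.00 | 3.00 | 1.67 | 0.34 | 5.66 |
| 30% / 30% | 3.00 | 3.00 | 1.00 | −1.00 | 7.00 |
| 25% / 15% | 2.33 | 3.67 | 1.34 | 0.34 | 5.66 |
| 30% / 10% | 1.67 | 4.33 | 1.00 | 0.34 | 5.66 |

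A simulation of 3,000 trials per scenario, with 100 imputations each, agrees. At 20% per arm it gives 2.95 for both same-direction runs and 0.25 and 5.65 for the opposed runs. At 25% / 15% it gives 2.36 and 3.61 for the same-direction runs.

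**Step 4: effect on significance.** A second simulation used 4,000 trials, baseline correlation 0.5 and one fixed fill per missing value. The shares significant in favour of MA&R are illustrative, since fixed fills are treated as observed data:

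| Missing MA&R / control | Both worst | Both best | MA&R only worst | MA&R worst, control best |
|---|---|---|---|---|
| 20% / 20% | 76% | 76% | 37% | 7% |
| 30% / 15% | 47% | 93% | 21% | 4% |

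At 20% / 20% the planned pair cannot be told apart, while a shift in MA&R alone halves the share.

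**Step 5: how far a shift must go.** With complete data the smallest significant difference is 1.979 × 6 × √(2/64) = 2.10. A shift of δ points in MA&R only moves the estimate by m_T × δ. Going from 3.00 to 2.10 therefore needs about 0.90/0.10 = 9 points at 10% missing, 4.5 at 20% and 3 at 30%. These are rough upper figures, because intervals from imputed data will be wider than with complete data.

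**The case against.** **Cancellation is conditional.** It needs similar loss and similar imputation spread. Section 5.9 expects that dropout may be skewed, and with higher loss in MA&R the both-worst run is a real stress: at 30% / 15% the simulated difference falls to 2.07 and fewer than half of trials stay significant. Fixed fills also change the variance, so a p-value can move even when the means cancel (76% significant against 82% with mean imputation at 20% / 20%). This stands. What the run responds to, however, is mainly the dropout imbalance and not how the non-responders fared. With 15% missing in MA&R and 25% in control, both-worst would raise the estimate to 3 + 6.66 × 0.10 = 3.67.

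**The imputation model is a defence.** Section 5.9 adds auxiliary variables, predictors of missingness and at least 100 imputations. This makes missing at random more credible. It does not test it.

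**Opposed fills are near-extreme.** Placing every missing MA&R participant at the 10th percentile and every missing control at the 90th would overturn many trials with 20% to 30% loss. This stands too: the opposed figures are outer bounds, and a graded shift is more informative.

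**Stronger readings.** A reader might infer that the primary result will look robust whatever happened to MA&R non-responders, or will be reported as robust. The SAP supports neither: unequal loss does move the estimate, and section 5.5 sets no rule for interpreting these runs. A reader might also take the registration of MA&R dropout in section 4.3.1 as evidence of arm-specific missing outcomes. That section concerns leaving treatment, and such a participant may still answer the questionnaire and be observed.

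**Conclusion.** The point holds in a limited form. With the percentiles read as 10th and 90th, the two planned scenarios leave the mean difference nearly unchanged when loss and imputation spread are similar in the arms; otherwise they mainly reflect the dropout imbalance. No planned analysis tests an arm-specific departure from the assumption on which section 5.4.2 makes validity depend.

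The gap in the illustrative case (20% missing per arm) is no movement in the planned runs against up to 2.66 points in the opposed ones, compared with a target difference of 3. The size depends on the assumed loss, R-squared and fills; the direction of the argument does not. The primary estimate and test are unaffected. This is a cheap improvement to a supporting analysis and should be made.

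**What to change.** In section 5.5, keep the same-direction pair, labelled as descriptive, and add for the primary outcome, on the existing imputed datasets:

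1. Shift the imputed POES-S values downward in MA&R only, in fixed steps.
2. Separately, shift them upward in control only. A downward shift in control would favour MA&R and would not stress a positive result.
3. Continue each series until the 95% CI first includes zero or the 9–36 scale limit is reached, and report that tipping point. Do not fix a short grid in advance: Step 5 of the working shows that with low loss the tipping point may lie many points away.
4. If the primary result is not significant, report the estimates across the grid.
5. If the percentile format is kept, add the two opposite-direction runs and describe them as outer bounds.

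The same rewrite can correct the duplicated percentile. The cost is a few lines of SAP text and a few more runs. The downside is that the primary result may look less robust.
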